## 8.7. General Statistical Considerations

All collected study data will be presented in subject data listings. Statistical analyses will be performed using SAS® for Windows, version 9.2 or later. Descriptive statistics (n, mean, standard deviation, median, minimum and maximum) will be calculated by treatment group for continuous variables. Frequencies and percentages will be presented by treatment group for categorical variables.

## 8.8. Subject Disposition

The disposition of all subjects who sign an ICF will be provided. The numbers of subjects screened, randomized, completed, and discontinued during the study, as well as the reasons for all post-randomization discontinuations will be summarized by treatment group, for all centers combined and each center separately. Disposition and reason for study discontinuation will also be provided as a by-subject listing.

## 8.9. Demographic and Baseline Characteristics

Demographics and baseline characteristics will be summarized by treatment group using appropriate descriptive statistics.

## 8.10. Analysis Populations

### 8.10.1. Intent-to-Treat Population

The Intent-to-Treat (ITT) population is defined as all randomized subjects. The Intent-to-Treat population will be the primary population for the analysis of the primary and secondary endpoints.

### 8.10.2. Per Protocol Population

The Per Protocol (PP) population is defined as all randomized subjects who were not associated with a major protocol violation. This population will be identified before the database lock. The PP analysis of primary and secondary endpoints will be considered supportive.

For the per protocol analysis, no data points will be imputed, all missing values will remain as missing.

### 8.10.3. Safety Population

The Safety population is defined as any subject receiving the allocated treatment after randomization. This population will be used for the analysis of safety parameters.

## 8.11. Statistical Methods

A Statistical Analysis Plan (SAP) will be developed and approved before the database is locked. The SAP will present the detailed statistical methodology to be used in analyzing the efficacy and safety data from this trial.

## 8.12. Efficacy Analyses

### 8.12.1. Primary Analysis

Primary Endpoint: The primary analysis will be conducted on the ITT population. The proportion of subjects with confirmed closed study ulcers during the treatment phase of the study, as assessed by the investigator, will be compared using the *Cochran–Mantel–Haenszel (CMH)*. For the primary efficacy analysis, missing values will be imputed using last observation carried forward.

For the primary analysis, the first date of assessment of 100% re-epithelialization of the ulcer surface without detectable exudate will be used.

The Breslow-Day test will be used to assess the homogeneity of the primary endpoint across study sites. If the Breslow- Day test concludes lack of homogeneity

(at a two-sided alpha level of 0.10), additional exploratory analyses will be performed to characterize the differences in results among sites.

Secondary Endpoints: To maintain the trial-wise Type I error rate at 0.05, a closed test procedure will be used for the secondary endpoints. For efficacy analyses, the first date of assessment of 100% re-epithelialization of the ulcer surface without detectable exudate or visible non-epidermal tissue will be used.

The order of the endpoints will be as follows:

1. Proportion of subjects with confirmed complete wound closure of the study ulcer during the 12-week treatment phase as assessed by computerized planimetry, during the treatment phase
2. Time to complete wound closure, as assessed by the investigator.
3. Time to complete wound closure, as assessed by computerized planimetry.
4. Rate of ulcer closure as assessed by computerized planimetry.

Prognostic Factors Assessments: For the Intent-to-Treat population, a covariate analyses will be conducted to assess the impact of various prognostic factors on ulcer closure and also to demonstrate the robustness of the primary analysis. Prognostic factors (i.e., covariates) will be included if they are found to be contributing factors (i.e., the individual covariate p-value is less than 0.05). Potential prognostic factors to be considered include:

- Baseline ulcer size
- DM type
- Age of ulcer at baseline
- Race
- Gender
- Nicotine Use
- Recorded HbA1c
- Baseline BMI
- Ulcer location

Additional planned analyses include the use of Analysis of Covariance (ANCOVA) models which incorporate consideration of stratification factors (i.e., site and baseline ulcer area) in order to compare reduction in study ulcer size between the two treatment groups and Kaplan-Meier analysis to assess and describe the differences in the time to ulcer closure in the two treatment groups.

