#### 8.3. Sample Size Determination and Rationale

This is a randomized study with two treatment groups. Assuming:

- 46% of DFUs receiving PriMatrix close by 12 weeks (84 days).
- 26% of DFUs receiving with SOC close by 12 weeks (84 days).

Overall 2-sided Type I Error rate (alpha) of 0.05. Under the above assumptions, 102 subjects per treatment group will be required to meet the Type I error rate of 0.05 and 80% power; for a total of 204 subjects for the study. As the treatment duration is short, the discontinuation rate is predicted to be around 15%. To accommodate the potential discontinuations, 256 subjects will be randomized (128 per treatment group) to this trial. The subjects will be randomized to the treatment groups in a 1:1 ratio.

A single interim analysis when 50% of subjects complete the trial, using group-sequential methods and Pocock alpha spending function, where the hypotheses will be tested at a two-sided alpha of 0.031 at the interim analysis and at a two-sided alpha of 0.028 at the final analysis.

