#### 8.4. Randomization

The randomization will be stratified by center and will use mixed blocks of 2 and 4 with a 1:1 ratio of Active Treatment to Control Treatment to ensure even distribution of Active and Control subjects at each site. Trial ulcer size (area) at the time of randomization (2 strata: 1 cm^2 to ≤3 cm^2 vs. >3 cm^2 to 12 cm^2) will also be used as a stratification factor to ensure balance between each treatment group in this stratum.

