11.4. Prognostic Factors Assessments

For the ITT population, a covariate analysis will be conducted to assess the impact of various prognostic factors on ulcer closure and to demonstrate the robustness of the primary efficacy analysis. Prognostic factors (i.e., covariates) will be included if they are found to be contributing factors (i.e., the individual covariate p-value is less than 0.05). Potential prognostic factors to be considered include:

Baseline ulcer size	Diabetes type
Age of ulcer at baseline	Race
Gender	Nicotine Use
Recorded HbA1c	Baseline BMI
Ulcer volume	Ulcer location

Additional planned analyses include the use of Analysis of Covariance (ANCOVA) models which incorporate consideration of stratification factors (i.e., site and baseline ulcer area) to compare reduction in study ulcer size between the two treatment groups and Kaplan-Meier analysis to assess and describe the differences in the time to wound closure in the two treatment groups.

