13.2.3. Other Variables

Discontinuations

The difference between treatments, both overall and for each primary reason, will be compared by using a 2-sided Fisher's exact test.

Demographic and Baseline Characteristics

Comparisons between treatment groups of continuous variables will be made by using a one-way analysis of variance with treatment as a factor. For categorical variables, the Fisher's exact test will be used. All tests will be 2-sided and performed at the 0.05 level of significance.

Time-to-Event Data

Time-to-event endpoints including time-to-complete-wound-closure/healed will be evaluated using the Kaplan-Meier method. The log-rank test will be used to compare the distributions between two treatment groups, stratified by the ulcer size (1 cm² to ≤ 3 cm² vs. > 3 cm² to 12 cm²).

Rate of Wound Closure, as Assessed by Computerized planimetry

Analysis of Covariance (ANCOVA) will be used to compare the rate of wound closure (as defined in section 13.2.2 for the two treatment groups. The stratification factor, ulcer size at the time of randomization, will be used in this analysis. Other covariate, as outlined in section 11.4, may also be incorporated in the model, if their presence is statistically significant (i.e. p-value ≤ 0.05).

Safety Data

The primary safety endpoint for this study is any severe device-related complication where relationship to the device was assessed by the clinical event committee possible, probably, or definite. Fisher's exact test will be used to compare incidence rates of serious device-related complications as well as for any device-related complication, and for specific complications between the treatment group and the control group.

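### The SAP's ANCOVA for rate of wound closure omits site, a randomisation factor that the companion ANCOVA of ulcer-size reduction includes; reconcile the two and fix the covariates in advance (minor)

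*Protocol*

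**What the plan says.** Allocation: Protocol 8.4 states "The randomization will be stratified by center and will use mixed blocks of 2 and 4", and adds ulcer area at randomisation as a second stratification factor, with a cut at 3 cm². SAP 7 repeats this.

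Endpoint: rate of closure by planimetry is fourth and last in the ordered secondary endpoints (Protocol 8.12.1, SAP 11.2). SAP 13.2.2 defines it as 7 × (baseline size − post-baseline size) / (baseline size × days in trial).

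Two ANCOVAs are described:

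- Reduction in ulcer size. Protocol 8.12.1 plans models "which incorporate consideration of stratification factors (i.e., site and baseline ulcer area) in order to compare reduction in study ulcer size". SAP 11.4 has the same content: "stratification factors (i.e., site and baseline ulcer area) to compare reduction in study ulcer size between the two treatment groups".
- Rate of wound closure. The protocol synopsis names an ANCOVA without covariates. SAP 13.2.3 supplies the model: "The stratification factor, ulcer size at the time of randomization, will be used in this analysis". It then lets covariates from SAP 11.4 be added if their p-value is 0.05 or less. That list contains baseline ulcer size but not site.

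**The concern.** The sponsor treats site and baseline area as the adjustment factors for size reduction. It then drops site for a closely related outcome that carries a place in the alpha-controlled sequence. No reason is given.

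Blocking within site largely removes between-site differences from the treatment contrast. If site is then left out of a linear model, those differences stay in the residual variance. The reported standard error is larger than the true sampling variability, so the test rejects too seldom under the null and loses some power under the alternative.

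Baseline area raises a second, smaller issue. In the fixed part of the model it appears only as a two-level stratum. Whether the measured value is used depends on a significance test in the trial data, so the model for a ranked test is not fully known in advance.

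**Working it through.** **1. The plan's own figure.** The documents give no SD, effect size or power for the rate endpoint. The only sample-size figure concerns the binary primary endpoint. Inputs from Protocol 8.3 are "46% of DFUs receiving PriMatrix close by 12 weeks (84 days"), "26% of DFUs receiving with SOC close by 12 weeks (84 days"), 80% power, and "two-sided alpha of 0.031 at the interim analysis and at a two-sided alpha of 0.028 at the final analysis". At the final level of 0.028:

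n per group = (2.197 + 0.842)² × (0.46 × 0.54 + 0.26 × 0.74) / 0.20² = 101.8, so 102.

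This matches the stated 102. The power of the interim look with 51 per group at 0.031 is 0.478, against the stated 0.479. Both reproduce, and neither bears on the ANCOVA.

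**2. Direction and ceiling of the effect.** Let s be the share of the residual variance that is due to site. With perfect balance within sites, the model standard error exceeds the true one by a factor 1/√(1 − s), and a nominal 5% test has true size 2 × [1 − Φ(1.96/√(1 − s))]:

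| s | SE ratio | True size |
|---|---|---|
| 5% | 1.026 | 4.4% |
| 10% | 1.054 | 3.9% |
| 15% | 1.085 | 3.4% |
| 20% | 1.118 | 2.8% |

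Incomplete blocks at small sites weaken this. In simulation the model standard error was about 1-4% too large at a 10% site share and 8-10% too large at 20%.

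**3. Power.** Inputs from the documents: 207 patients (SAP 11.1.1), up to 30 sites (synopsis), and blocks of 2 and 4 within site and size stratum (Protocol 8.4). Assumptions: unequal site sizes, normal outcome, common treatment effect of 0.39 SD, test level 0.05, and the variance shares shown. Sites with fewer than 6 patients are pooled in the proposed model. Two separate sets of 2,000 simulated trials per row gave the following power (Monte Carlo error of each figure just under 1 point):

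| Set | Site / area share | Treatment + size stratum | SAP rule (area added if p ≤ 0.05) | Pooled site + log area + stratum | Proposed minus SAP rule |
|---|---|---|---|---|---|
| 1 | 0 / 0 | 80.1% | 80.1% | 79.2% | −0.9 |
| 1 | 5% / 5% | 81.5% | 82.3% | 82.6% | +0.3 |
| 1 | 10% / 10% | 83.9% | 84.7% | 86.8% | +2.1 |
| 1 | 10% / 20% | 86.1% | 88.2% | 90.3% | +2.1 |
| 1 | 15% / 20% | 87.5% | 89.7% | 92.0% | +2.3 |
| 2 | 2% / 5% | 83.6% | 83.3% | 83.0% | −0.3 |
| 2 | 5% / 10% | 82.8% | 83.9% | 84.6% | +0.7 |
| 2 | 5% / 20% | 84.4% | 86.8% | 87.4% | +0.6 |
| 2 | 10% / 20% | 86.6% | 89.7% | 91.0% | +1.3 |
| 2 | 15% / 20% | 88.0% | 89.6% | 92.6% | +3.0 |

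The fair comparison is the last column, because the SAP already allows baseline size to enter. Differences below a point cannot be told from zero.

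**4. Type I error.** At 15% / 20% it was 3.5% for the stratum-only model, still 3.5% under the SAP rule, and 5.0% for the proposed model. The selection rule recovers much of what the dichotomy of area loses, but it cannot recover site.

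**5. Why the pooling matters.** Unpooled fixed site effects use about 28 degrees of freedom. If neither factor explains anything, power with unpooled sites in set 1 falls from 80.1% to 77.2%; with pooling it falls to 79.2%.

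**The case against.** **The two descriptions may be one analysis.** Rate is size reduction scaled by baseline size and time, so Protocol 8.12.1 and SAP 13.2.3 could be read together, which would put site in the model. SAP 13.2.3 also refers to section 11.4, whose next paragraph names site. This does not remove the problem. SAP 13.2.3 is the specific text for the rate endpoint, names one factor in the singular, and points to covariates in a list that lacks site. The ambiguity is itself a reason to reconcile the text.

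**Measured area is not discarded.** A reader might infer that baseline area is reduced to two levels for good. The documents do not support that: baseline ulcer size may enter under the p-value rule. What stands is that its use depends on the data.

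**The loss may be nil.** A reader might also infer that the error bars are certainly too wide and power is certainly lost, or take the gain of about 4 points over the stratum-only model at 10% / 20% as the size of the problem. Neither follows. The documents give no variance share for site or area, the gain over the SAP's own rule is smaller, and at a site share of about 5% or less it disappears. The rate is already divided by baseline size, so the 20% area share may be generous, and a rate per week may be skewed rather than normal.

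**The consequence is limited.** The error is in the conservative direction and touches only the last of four ordered secondary tests. All of this stands and sets the severity.

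**Conclusion.** The omission of site from the rate ANCOVA is real, and it conflicts with the companion ANCOVA and with the randomisation. Its effect is conditional. If site is prognostic, the standard error is too large and the test conservative: type I error is about 3.5% rather than 5% at assumed shares of 15% for site and 20% for area. Power is then about 1 to 3 points below the proposed model at a site share of 10-15%, and not distinguishably different at about 5% or less. These figures rest on assumed variance shares, a normal outcome, an effect of 0.39 SD and testing at 0.05.

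Severity is minor. The point concerns the precision and prespecification of the final ordered secondary test. It does not affect the primary endpoint or the sample size, and it carries no false-positive risk.

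**What to change.** In SAP 13.2.3, state that the rate ANCOVA contains treatment, site, the ulcer-size stratum, and log baseline ulcer area as a continuous covariate, and that none of these terms is selected by p-value. Pool sites with fewer than 6 subjects, extending to this model the rule that SAP 11.1 gives only for the Breslow-Day test. Specify the post-debridement area at randomisation, since Protocol 6.2.1 takes readings both before and after debridement that day. Use the same terms in the ANCOVA of ulcer-size reduction in Protocol 8.12.1 and SAP 11.4.

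The cost is a sentence in the SAP, matching wording in the other two places, and no new data. The model spends some degrees of freedom, which costs about 0 to 1 point of power if site and area explain nothing.

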#### 8.12.2. Exploratory Analyses

An exploratory analysis will be performed to assess costs associated with the management of DFUs for the active and control groups using medical resource utilization data and standardized direct and in-direct unit costs. Additionally, ulcer closure status at the 4-week follow up visit will be evaluated.

### 8.12.3. Treatment Failures

Subjects who are withdrawn or discontinued during the treatment phase and/or who do not achieve complete wound closure during the treatment phase will not be replaced and will be considered treatment failures.

For missing data that are used in continuous data analyses, the last available observation (LOCF) will be used. In the analyses using the planimetry data, the last available planimetric value will be used for discontinued subjects.

### 8.12.4. Safety Analyses

The Safety population will be used for the analysis of safety endpoints.

Safety will be assessed through reports of AEs and SAEs. AEs related to the device, study ulcer and/or study procedures and all SAEs will be recorded.

All safety parameters will be summarized descriptively by treatment. No inferential statistics are planned.

### 8.12.5. Adverse Events

AEs will be coded using the MedDRA Medical Dictionary. Treatment Emergent AEs (TEAEs) are defined as events with an onset on or after the first randomized treatment. TEAEs will be summarized by treatment group, System Organ Class, and preferred term. The following TEAE summaries will be provided:

- TEAEs by severity grade
- TEAEs by relationship to study treatment.

In addition, separate summaries of SAEs, and AEs resulting in discontinuation of study treatment will be presented.

### 8.12.6. Supportive Analysis

To assess the robustness of the primary analysis results, supportive analysis will be conducted using the PP population. Statistical methodology for the supportive analyses will be the same as that of the primary analysis, with the exception of the analysis population used. The PP population will be used for the supportive analysis while ITT population will be used for the primary analysis. Subjects in these populations with no post randomization data for the primary endpoint will be considered NOT CLOSED, i.e., treatment failures, in this analysis.

## 9. Direct Access to Source Data/Documentation

The monitors, auditors, personnel authorized by the sponsor, and regulatory and health authority inspectors or their agents will be given direct access to source data and documentation (e.g., medical charts/records, printouts, videotapes, etc.) for source data verification, provided that subject confidentiality is maintained in accordance with local requirements. Access to electronic medical

records may be governed by institution policy and each site will be required to ensure access to medical records as allowed by institutional requirements.

## 10. Quality Control and Quality Assurance

### 10.1. Monitoring Requirements

In an effort to fulfill the obligations outlined in ICH guidelines which requires the sponsor to maintain current personal knowledge of the progress of a study, the sponsor has developed a Monitoring Plan in order to establish and document practical methods for the clinical team in monitoring and maintaining adequate study oversight. The sponsor's designated monitor will visit the center(s) during the study as well as maintain frequent telephone and written communication. The investigator will permit the sponsor to monitor the study as frequently as is deemed necessary and provide access to medical records to ensure that data are being recorded adequately, that data are verifiable, and that protocol adherence is satisfactory.

The investigator will permit representatives of the sponsor and/or designated CRO to inspect all eCRFs and corresponding study subject original medical records (source documents) at regular intervals throughout the study. Subject original medical records and other relevant data must be available to support all data recorded in the eCRF. In addition to the original medical records, these data may include but is not limited to, study, laboratory and diagnostic reports, ulcer images and tracings, diary pages, quality of life questionnaire, etc.

Site inspections serve to verify strict adherence to the protocol and the accuracy of the data being entered on the case report forms, in accordance with federal regulations. A Monitoring Log will be maintained at each study site which the monitor will sign, date and state the type of visit.

The investigator should be aware that the study site and subject records may be inspected by the sponsor or other representatives or other regional regulatory authorities.

For any data transfer through e-mail, the data file(s) will be password protected; the password will be exchanged in the separate e-mail or by phone.

For the Interim Analysis, a cut-off date for data collection and monitoring will be determined and sites will be requested to provide current information up to the cut-off date.

The final statistical analysis of data will be performed after all clinical monitoring has been completed, all data queries have been resolved, and all data have been verified (QC) prior to formal database lock. The sponsor will authorize the final database lock for all sites.

## 10.2. Acceptability of Case Report Forms

Electronic Case Report Forms will be used for the collection of data via electronic data capture (EDC). An eCRF must be completed for each subject who has signed an ICF. For subjects who are screen failures, this would be limited to the screen failure eCRF page. All source documents and eCRFs will be completed as soon as possible after the subject's visit. Corrections to data on the eCRFs will be documented in the electronic audit trail which is 21 CFR Part 11 compliant. The investigator will review eCRFs to indicate that, to his/her knowledge, they are complete and accurate. eCRFs will be reviewed by the sponsor/designee who will make a decision as to their acceptability.

## 10.3. Reporting Protocol Deviations

The investigator is obligated to follow the protocol without departure from the requirements written in the protocol. If the investigator deviates from the protocol requirements, the sponsor will make the determination as to whether the subject will continue in the study. The sponsor also has the right to discontinue the subject for protocol violations. The IRB may also have to be contacted if safety to the subject or if the scientific soundness of the study is involved. All protocol deviations must be documented in the eCRF.

